In Stage 1, subjects will be randomly assigned to receive two experimental psychotherapy sessions assisted by either active placebo MDMA (3 subjects) or full dose MDMA (5 subjects). Subjects who receive the active placebo dose of MDMA will be offered the option to enroll in the open-label Stage 2 unless they meet any exclusion criteria for study participation. In Stage 2, subjects will receive full dose MDMA and the experimental sessions will otherwise follow the same sequence of events after a single preparatory session. (See Table 3 Time and Events)

All outcome measures will be assessed by a blinded independent rater. The independent rater will assess PTSD symptoms with the CAPS and PDS, quality of life with the GAF, symptoms of depression with the BDI-II, and sleep quality with the PSQI. The subjects will complete the PDS, a self-report measure of their PTSD symptoms, to provide correlations with measures administered by the independent rater. The PDS will be completed at baseline, during every third integrative session after an experimental session, and at the end of each Stage. Baseline assessments will be compared with assessments made in Stage 1.

All subjects will complete a follow-up occurring 2 months after their last experimental session in Stage 1 and Stage 2, if applicable. The blind will be broken for all subjects in Stage 1 after completing this assessment. In addition all subjects will complete a visit 12 months after their final experimental session where outcome measures and a questionnaire on any lasting benefits or harms of the treatment will be administered.

At each visit with the therapists, the subject's general wellbeing and suicidality will be assessed with the Columbia Suicide Severity Rating Scale (C-SSRS). Adverse Events and Concomitant Medications will be collected as described in Section 8.5 and 9.0 of the protocol.

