5.1.2 Safety Measures

Safety measures, vital signs and a measurement of psychological distress will be assessed during all experimental sessions. Subjects will rate their current degree of subjective distress with a single-item, self-report scale, the SUD scale, repeatedly during the experimental sessions, with the degree of distress marked along seven points.

The C-SSRS (Hebrew translation) is a clinician-administered measure of suicidal behavior devised to detect potential suicidal thoughts or behaviors during a clinical trial [92]. It consists of a "Baseline" form that assesses lifetime suicidal ideation, ideation intensity and behavior, and a form for assessing current suicidal ideation and behavior. The C-SSRS consists of a series of questions, and can be administered during a face-to-face interview or over the telephone. Suicidality will be assessed at baseline, once during any face-to-face visit, during the second and seventh days of telephone contact, and twice during each experimental session. Subjects who are discontinuing medication to participate in the study will complete the C-SSRS before and after medication washout. The C-SSRS data will be collected on Case Report Forms (CRFs) for all administrations except for the second integrative session, unless an increase in suicidality is observed by the therapists. C-SSRS data from the second integrative session after each experimental session will be kept with the subject's source record.

The therapists will assess general wellbeing during each preparatory session, on each integrative session and integrative telephone calls for seven days.

Blood pressure and heart rate will be assessed periodically during each experimental session. Blood pressure and pulse will be measured at the outset of the experimental session, and once approximately every 30 minutes during the experimental session. More frequent measures will be taken if the established thresholds of 160 systolic, 110 diastolic or pulse of 110 are exceeded. Blood pressure will also be measured more frequently if there are symptoms, such as chest pain, shortness of breath or neurological symptoms,

that may be indicative of hypertension. The therapists will measure subject body temperature approximately every 60 to 90 minutes. Cardiovascular effects will be assessed via blood pressure measurement. The timing of these measurements will be adjusted so they do not interfere with the therapeutic process.

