5.2 Study Procedures and Visit Descriptions

5.2.1 Prescreening, Screening and Baseline Evaluation (Pre-study)

All individuals who enter screening, as defined in this section, should be assigned a screening number and recorded on the "subject screening log" where information on the selection of potential subjects in the trial should be collected. The subject screening number should also be recorded on the subject's informed consent form. If a subject is enrolled, the study staff should record the enrollment date and assign a subject number. If a subject is not enrolled, an explanation should be recorded on the screening log. A CRF will not be completed for subjects who are not enrolled. These subjects will only be documented on the screening log and source records. It is the responsibility of the investigator to file the screening log in the investigator site file (ISF) to be readily available for on-site monitoring and/or inspection by relevant authorities. Screening may take place over more than one day and up to one month prior to Visit 1. If, after reviewing all information, the investigator concludes that a subject is eligible, he will enroll the subject in the study. Visits will be scheduled consecutively as described in the Time and Events Table.

- a. Explain and obtain written informed consent from the subject. Written informed consent must be obtained prior to performing any tests or evaluations for the study.
- b. Assign the subject a screening number. Complete the screening log.
- c. Subjects will provide a medical and psychological history.
- d. Review the ability of females of childbearing potential to become pregnant and their commitment to practice appropriate birth control as determined by the investigator for the total duration of the study.
- e. A physician will perform a general physical examination. The examination will involve the following procedures:
 - blood pressure
 - pulse
 - height
 - weight
 - body temperature

- examination of head, eyes, ears, nose, throat, skin, heart, lungs, abdomen and extremities
- brief neurological exam (cranial nerves 2-12, sensory, motor, reflexes and cerebellar function)
- electrocardiogram (ECG)
- serum electrolytes, metabolic profile, urinalysis and complete blood count
- Human Immunodeficiency Virus (HIV) serology
- Urine-dip pregnancy test on females with childbearing potential
- C-SSRS to assess suicide risk

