5.2.2 Preparatory Psychotherapy Sessions (Visits 1, 2 and 3)

Subjects who do not complete all screening activities will not be enrolled. If all inclusion criteria and no exclusion criteria are met, eligibility will be confirmed with the subject during Visit 1. After eligibility is confirmed, the subject will be enrolled during Visit 1 and issued a subject number. The first preparatory session will take place after enrollment during Visit 1. Remaining preparatory sessions will be scheduled as described in the Time and Events table.

Upon enrollment, subjects who must refrain from taking a psychiatric medication will begin tapering off that medication following a time course appropriate for the medication given its half-life, with the first experimental session scheduled to occur after complete washout. The therapists will perform the C-SSRS once after medication washout but prior to the first experimental session. This may occur during a scheduled administration of the C-SSRS during the second preparatory session, or at an additional time appropriate to the medication washout.

a. Record preparatory sessions to audio and video. Subjects may receive

- copies of audio or video recordings from these preparatory sessions upon request.
- b. AEs and Medications will be recorded as described in Section 8.5 and 9.0 of the protocol from the time the subject is enrolled at Visit 1.
- c. The therapists will inquire about any possible changes in the subject's health to ensure that subject continues to meet eligibility criteria and if applicable, will confirm that the subject has appropriately tapered off of medications.
- d. The subject will undergo three preparatory sessions lasting at least an hour with the therapists, who will be a male and a female co-therapist team. The therapists will work with the subject to prepare him or her for MDMA-assisted psychotherapy. The therapists and subject will seek to form a strong working relationship with each other, and they will help the subject prepare for upcoming experimental sessions. Preparatory sessions will promote a safe space for confronting trauma-related memories, emotions and thoughts. Subjects will remain with the therapist team they begin with throughout the study.
- e. The subject and therapists will discuss goals for the experimental session and will review what will happen during the experimental session, following standard procedures and techniques discussed in the Sponsor's treatment manual.

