- f. During one of the preparatory sessions the therapists will introduce the subject to the attendant that will remain with the subject during each overnight stay after each MDMA-assisted psychotherapy session. The attendant will be an individual with previous training in managing psychological distress.
- g. If a subject would like another individual present during or after the experimental session, a meeting between the therapists and that individual will be scheduled prior to the first experimental session. There must be mutual agreement between the subject and therapists concerning the presence of the support individual.
- h. Subjects will complete the C-SSRS just prior to beginning the second preparatory session, unless a subject is still undergoing medication washout. Subjects still undergoing medication washout will complete the C-SSRS during the second preparatory session or at a point after washout is complete.
- i. General wellbeing will be assessed at each preparatory session.
- j. AEs and medications will be collected as described in Sections 8.5 and 9.0 of the protocol.
- k. During the third and last preparatory session, the therapists will give the Subject Information Sheet to the subject, which includes instructions and restrictions for conduct 24 hours prior to receiving the drug, including restrictions on food and alcohol consumption. Subjects must agree to take:
 - Nothing by mouth except alcohol-free liquids after 24:00 (midnight) the evening before the experimental session.
 - Subjects must also refrain from the use of any psychoactive drug, with the exception of caffeine or nicotine, within 24 hours of each experimental session.
 - Subjects must not use caffeine or nicotine for 1 hour before and 3 hours after ingesting the drug, or until therapists deem it safe to do so.
 - Subjects must refrain from smoking marijuana for at least 3 days prior to the experimental session. They may smoke marijuana on the 8th day after the experimental session if needed. This will be collected with the Concomitant Medications.

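### Two C-SSRS rules conflict at the preparatory visits, and the deferral option in Protocol 5.2.2(h) lets a subject taper psychiatric medication with no structured suicidality assessment until washout ends

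*Protocol*

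**What the plan says.** Two general provisions in the Protocol call for the C-SSRS at every visit. Section 4.0 says that, whenever a subject sees the therapists, "general wellbeing and suicidality will be assessed with the Columbia Suicide Severity Rating Scale". Section 5.1.2 says: "Suicidality will be assessed at baseline, once during any face-to-face visit". V1, V2 and V3 are face-to-face sessions with the therapists, so both provisions reach them.

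The visit-level texts are narrower. Section 5.2.2(h) names only the second preparatory session. In Table 2 the C-SSRS cell for V1-V3 carries superscript H. The SAP's copy of the table shows that footnote as restricting the scale to V2.

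Subjects coming off medication have further rules:

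- Start of taper (5.2.2): "Upon enrollment, subjects who must refrain from taking a psychiatric medication will begin tapering off that medication". Enrollment is at V1.
- Taper rule (5.1.2): "Subjects who are discontinuing medication to participate in the study will complete the C-SSRS before and after medication washout".
- Post-washout check (5.2.2): "The therapists will perform the C-SSRS once after medication washout but prior to the first experimental session".
- Timing option (5.2.2(h)): "Subjects still undergoing medication washout will complete the C-SSRS during the second preparatory session or at a point after washout is complete".

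A C-SSRS is also given at screening. On its timing, 5.2.1 says: "Screening may take place over more than one day and up to one month prior to Visit 1". The first experimental session (V4) falls 3-5 weeks after V1 and has its own pre-dose C-SSRS.

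The only precedence statement is in SAP 5.0. It puts the Protocol above the SAP's design overview and does not rank one Protocol section against another.

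**The concern.** Entering the trial is what causes these subjects to stop their psychiatric medication. The taper is therefore a trial-induced risk period, and it is when one would most want a structured suicidality assessment. The general rule provides one at each preparatory visit. The visit-level rule provides one at V2 and then lets a subject still in washout postpone it. A site can comply fully with 5.2.2(h) and with the taper sentence in 5.1.2, and still give no C-SSRS between the start of the taper and the post-washout check.

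The main stake is subject safety. A smaller one is the safety tables. SAP 9.5 takes the C-SSRS baseline from preparatory session 2, or from V4 before dosing if that assessment was not done. A taper subject's baseline may therefore be a mid-taper or a post-washout value, depending on whether V2 was deferred.

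**Working it through.** The plan gives no figure to reproduce. The check compares the provisions and counts what each one requires.

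**Inputs.** V1 = day 0 (taper starts). Preparatory visits are about one week apart, so V2 = day 7 and V3 = day 14. V4 = day 21-35 (Table 2). The screening C-SSRS falls S days before V1, with S = 0-30. Assumptions: one month is 30 days and visits fall exactly a week apart. Taper length is not stated, so the end of washout is treated as a range.

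**Step 1: C-SSRS required across V1-V3.** Sections 4.0 and 5.1.2 give 3. Section 5.2.2(h) and footnote H give 1 for a subject not in washout.

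**Step 2: which text produces zero during taper.** Footnote H alone leaves the V2 assessment in place whether or not the subject is tapering. Zero arises only from the second option in 5.2.2(h), with the before-and-after rule in 5.1.2. The screening C-SSRS can serve as the assessment before washout.

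**Step 3: C-SSRS at V2 or V3 while washout is under way.**

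| Washout ends | Every visit | V2 only | V2 deferred |
|---|---|---|---|
| By day 7 | 0 | 0 | 0 |
| Day 7-14 | 1 | 1 | 0 |
| After day 14 | 2 | 1 | 0 |

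**Step 4: intervals without a C-SSRS.**

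- Every visit: the gaps are S, 7, 7 and (V4 - 14) = 7-21 days. The longest is 7 days (S = 0, V4 at day 21) to 30 days (S = 30).
- V2 only, not tapering: the gaps are S + 7 = 7-37 and (V4 - 7) = 14-28 days. The longest is 14 to 37 days.
- V2 deferred, counted from taper start: 14 days if the post-washout check is at V3; up to 21-35 days if washout ends just before V4.
- V2 deferred, counted from screening: 14 + S = 14-44 days if the check is at V3. If it is just before V4, 21-35 days with S = 0 and 51-65 days with S = 30.

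**Step 5: are V1 and V3 unusual?** A Stage 1-only subject has V1-V12 plus the 12-month visit, 13 in all. Under the visit-level texts, 11 carry a C-SSRS; V1 and V3 do not. With Stage 2 the count is 21 of 23, again without V1 and V3. These counts describe a subject who does not defer V2.

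**Step 6: administrations from screening through the V4 pre-dose assessment.** Every visit: screening + V1 + V2 + V3 + V4 = 5, or 6 with a separate post-washout check after V3. V2 only: screening + V2 + V4 = 3. Taper subject who defers: screening + post-washout + V4 = 3. The difference is 5 - 3 = 2, or 6 - 3 = 3.

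**The case against.** The best defence is that the specific text governs the general. Section 4.0 is a design overview. The sentence in 5.1.2 is loosely drafted, since it asks for one assessment at any face-to-face visit and then two at experimental sessions. The safety objective in 3.3 promises the scale at visits before experimental sessions without saying every visit. Section 5.2.2, footnote H and SAP 9.5 all point to V2, and 5.2.2 deals with washout expressly, so the timing looks deliberate. On this view, a cross-reference to the Time and Events table in 4.0 and 5.1.2 would cure the inconsistency.

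That is a possible reading, but no text adopts it, and it is the reading that leaves the taper uncovered. The cross-reference would remove the conflict and keep the gap.

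Some of the defence does stand. A reader might infer any of the following, and the documents do not support them:

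- *That the schedule itself allows no C-SSRS during taper.* Footnote H still places one at V2; only the deferral in 5.2.2(h) removes it.
- *That subjects go 65 days unassessed during withdrawal.* That figure combines the earliest screening, the latest V4 and washout ending just before V4, and 30 of those days precede the taper.
- *That suicidality goes unmonitored.* Serious suicide risk is excluded, and the C-SSRS is given at screening, after washout and before the V4 dose. Prescribers are consulted and psychiatric adverse events are collected. On wellbeing, 5.2.2(i) says: "General wellbeing will be assessed at each preparatory session".
- *That the three therapist teams will follow different schedules.* This is one monitored centre with a sponsor-supplied CRF, and nothing shows that practice would diverge.
- *That SAP 9.5 distorts a result.* Its two visit numbers for preparatory session 2 are a clerical slip, and the C-SSRS outputs are descriptive.

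**Conclusion.** The point holds. The Protocol has two C-SSRS rules for the preparatory visits and does not say which prevails. Through the deferral option in 5.2.2(h), a taper subject can have no C-SSRS between taper start and the post-washout check. That interval can reach about 21-35 days from taper start when washout ends just before V4, and 14 days when the check is at V3. Counted from screening, the extreme is 65 days. These figures rest on a 30-day month, weekly preparatory visits and V4 at day 21-35, and would lengthen if washout delayed V4. The documents do not say how many subjects will taper, so the number affected is unknown.

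The remaining safeguards are substantial, but none is a required structured suicidality assessment while medication is being withdrawn. The gap should be closed because the remedy is small and follows the Protocol's own general rule. It does not threaten the trial's efficacy conclusions.

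**What to change.** Amend 5.2.2(h) and footnote H, in the Protocol and SAP tables, so that the C-SSRS is given at V1, V2 and V3, as 4.0 and 5.1.2 already state. Remove the option to postpone V2 during washout. Keep the separate post-washout C-SSRS before V4. If the sponsor prefers a narrower change, the minimum is a C-SSRS at each preparatory visit for any subject in taper. The V1 assessment is worth including even though it falls at taper start, because the screening value may be up to a month old by then.

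As a minor consequential edit to SAP 9.5, correct the visit number for preparatory session 2 from 3 to 2. Keep V2 as baseline for subjects not tapering. For taper subjects use the first post-washout, pre-drug C-SSRS, or the V4 pre-drug value if there is no earlier one.

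The cost is a protocol clarification, a short SAP edit and two extra short administrations per subject at existing visits, or up to three for a taper subject who would have deferred V2. For ten subjects that is 2 x 10 = 20 if none would have deferred and at most 3 x 10 = 30 if all would. Each replacement subject adds two or three, and each administration needs CRF entry.

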5.2.4 Integrative Sessions 24 Hours after Experimental Session (Visits 5 and 9)

- a. On the morning after each experimental session, both of the therapists from the subject's team will meet with the subject during a 90-minute integrative therapy session.
- b. The entire integrative psychotherapy session will be recorded to audio and video. Subjects may receive copies of this session upon request.
- c. Subjects will complete the C-SSRS just prior to beginning each integrative session.
- d. Prior to integrative psychotherapy, the subject and both therapists will indicate their beliefs concerning subject condition assignment.
- e. Discuss and review events that occurred with the subject during the integrative session, including thoughts, feelings and memories. If necessary, the therapists will help the subject to reduce any residual psychological distress he or she is

- experiencing. The therapists will also encourage the transfer of states of acceptance, feelings of intimacy, closeness and reduced fear experienced in experimental sessions to emotionally threatening everyday situations. The therapists will be supportive, validating the experience and facilitating understanding and emotional clearing.
- f. The therapists will remain accessible any time the subject needs support outside the scheduled integration sessions.
- g. Assess the subject's mental health and the presence of any remaining reactions during integrative psychotherapy immediately after each experimental session.
- h. Integrative psychotherapy sessions can also serve as an opportunity for the therapists to gather information about the effects of the drug on the subject in an unstructured manner.
- i. After the integrative psychotherapy sessions, a person previously selected by the subject will provide a ride home to the subject. If the subject is unable to locate an individual willing or able to take him or her home, or if the designated person is unable to assist the subject due to unforeseen events, the therapists will assist the subject in finding an alternative means of returning home.
- j. Spontaneously reported reactions, Adverse Events and Medications will be collected as described in Sections 8.5 and 9.0 of the protocol.
- k. Remind the subjects that they will have daily contact for the next 7 days.

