5.2.5 Daily Telephone Contact for Seven days after an Experimental Session

- a. Starting on the day of the integrative psychotherapy session following each experimental session, one of the therapists will contact the subject via telephone or in person on a daily basis for one week.
- b. The integrative contact will be for a brief check-in lasting 5 to 15 minutes, or as long as necessary to address any subject's concerns and to assess subject's well-being. Additional telephone contact can be initiated at the request of the therapists or subject.
- c. On the second and seventh day of contact after the experimental session, the subject will complete the C-SSRS.
- d. General wellbeing will be assessed at each phone call.
- e. Spontaneously reported reactions, AEs and Medications will be collected as described in Sections 8.5 and 9.0 of the protocol.

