5.2.6 Integrative Psychotherapy Between Experimental Sessions (Visits 6, 7, 10 and 11)

- a. The subject will have two additional integrative psychotherapy sessions lasting at least an hour with at least one of the therapists from the subject's therapist team between each experimental session. The therapists may conduct more sessions if they and the subject deem it necessary.
- b. Record each integrative session to audio and video. Subjects may receive a copy of one or more integrative sessions upon request.

- c. The C-SSRS will be administered just prior to beginning each integrative session.
- d. General wellbeing will be assessed at each integrative session.
- e. The subject will complete the PDS questionnaire on the third integrative session.
- f. The subject and therapists will continue to work on supporting the subject as she or he considers his or her experiences during experimental sessions.
- g. The therapists will use clinical judgment to assess the subject's psychological wellbeing during this period of time. If there are any indications of continuing anxiety or distress, the therapists may arrange to work on reducing the distress at a specially scheduled integrative therapy session, through continuing contact, or at the next regularly scheduled integrative therapy session. The subject may also initiate contact with the therapists at any time throughout the study.
- h. AEs and medications will be collected as described in Sections 8.5 and 9.0 of the protocol.
- i. If an integrative session falls within the period of telephone contact and additional phone call is not required that day, all things normally collected during the telephone call will be completed in person.

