A =First Integrative session is 1 day after Exp. session B =Only on Visit 1 C = At least 24 hrs prior to exp. session D =Approximately 6 hours post MDMA E =At the beginning of the session F =As needed G =Approximately every 60 minutes H=Given on 2nd preparatory session only (V2) I= At 1st integrative visit after each Exp. Session for subjects & therapists and at V12 for the independent rater J = For 7 days post Exp. Session, CSSRS D2 and D7 of calls only, General well being for all 7 days K= Spontaneously reported reactions will be collected on the day of MDMA administration and for seven days after each Exp. Session. L= Determine after completion: Go on to Long-term follow up or Stage 2 M= Only for subjects not going to Stage 2 N= Subjects will complete PDS on third integrative session only

Table 3. Time & Events MP9 Stage 2	Preparatory	Experimental Session 1		Experimental Session 2		End of Stage 2		Long Term Follow-Up
Visit #	V13*	V14	V 15, 16, 17	V18	V 19, 20, 21	V22	1	1 Year Follow-up
Type of Visit	Preparatory Session	Experimental Session 1	Integrative Sessions	Experimental Session 2	Integrative Sessions	Follow-Up & Outcome		Follow-Up & Outcome
Visit Timing or Study day or Window	Within 1 month of V12*	1 week post V13	Approx. 1 week apart ^A	3-5 weeks post V14	Approx. 1 week apart ^A	May happen over more then 1 day. 2 months post V17	0	May happen over more then 1 day. One Year After V8 or V17
Confirm Informed Consent	Х						e	
Confirm Inclusion/Exclusion	X						tag	
Entry into Stage 2	Х						Ś	
Collect Concomitant Medication	Х	Х	Х	Х	Х	Х	6	Х
Record to Audio/Video	Х	Х	Х	Х	Х		e 1	
General Well-Being	Х	X ^B	Х	X ^B	Х	Х	tag	Х
Drug Screen		Х		Х			Š	
Pregnancy Screen (if applicable)		Х		Х			fteı	
CAPS, GAF, PSQI, BDI-II (with Ind. Rater)	Use V12*					Х	0.8	Х
C-SSRS	X	X ^{B, C, D}	Х	X ^{B, C, D}	Х	Х	dn	Х
Administer IP Drug + Therapy		Х		Х			M	
Monitoring of BP, Pulse and Temp.		Х		Х				
SUD		X ^{C, E}		X ^{C, E}			\mathbf{F}_{0}	
Overnight Stay		Х		Х			E	
PDS	Use V12*		X ^H		\mathbf{X}^{H}	Х	ler	Х
Integrative Therapy Session			Х		Х		ြည	
7 days Integrative Telephone Contact			X ^F		X ^F		10	
AEs Requiring Medical Attention	Х	Х	Х	Х	Х	Х		
Spont. Reactions and all AEs		X ^G	XG	X ^G	X ^G			
AEs related to changes in psychiatric status or withdrawal	Х	Х	Х	Х	Х	Х		Х
Serious Adverse Events	Х	Х	Х	Х	Х	Х		Х
RRPQ						Х		
Issue Memory Aid Card						X		
Follow up Questionnaire								Х
Termination Visit								Х

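### C-SSRS forms from the second integrative session reach the CRF only when an increase is observed, while SAP 9.9.4 tabulates levels by period: a small capture gap that is cheap to close

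*Protocol*

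**What the plan says.** **Administration.** Protocol 5.1.2 schedules the C-SSRS at baseline, "once during any face-to-face visit, during the second and seventh days of telephone contact", and twice in each experimental session. Section 5.2.4(c) covers the next-day session: "Subjects will complete the C-SSRS just prior to beginning each integrative session". Section 5.2.6(c) covers the two later ones: "The C-SSRS will be administered just prior to beginning each integrative session". Section 5.2.5(c) covers the calls: "On the second and seventh day of contact after the experimental session, the subject will complete the C-SSRS".

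**Data capture.** Protocol 5.1.2 has C-SSRS data entered on CRFs "for all administrations except for the second integrative session, unless an increase in suicidality is observed by the therapists". It then says where the excepted forms go: "C-SSRS data from the second integrative session after each experimental session will be kept with" the subject's source documents. Neither document says what an increase is measured against.

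**Analysis.** SAP 9.9.4 counts ideation as positive when the score is above 0, ideation as serious when the score is 4 or 5, and behavior as positive when its score is above 0. It tabulates number and percent by Stage 1 group and time period. It also compares lifetime serious ideation and positive behavior with cumulative on-study frequencies. SAP 9.5 defines the lifetime and baseline periods; the SAP text does not list the later ones or their denominators. It does not mention the capture exception. Protocol 3.3 and SAP 4.3 make suicidality a safety objective to be compared between conditions.

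**The concern.** The capture rule and the table use different criteria. Entry depends on a change that the treating therapists notice; the table counts a level. A subject whose ideation is present but unchanged at this contact is a positive by the SAP's definition, yet produces no CRF record. A subject with no ideation produces none either, so the negatives that belong in a denominator are also missing. What remains at this contact is a subset chosen by a judgement about suicidality itself.

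The scale is completed at the visit whatever the result. The gap therefore comes from a data-entry rule, not from a missed assessment. At stake is the accuracy of a descriptive safety table on a named safety objective. The primary CAPS analysis is not touched.

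**Working it through.** The documents give no figure for this point, so the check is a count of forms and a comparison of the two rules.

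**1. Visits affected.** In the Time and Events tables, V5–V7 and V9–V11 are the integrative sessions in Stage 1, and V15–V17 and V19–V21 in Stage 2. The second of each set is V6, V10, V16 and V20.

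**2. Scheduled Stage 1 forms per subject.** For the preparatory visits I count V2 alone, as footnote H of SAP Table 2 states: "Given on 2nd preparatory session only". Protocol 5.2.2(h) agrees. Extra forms around medication washout are not counted.

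- Before the first dose: screening 1 + V2 1 + V4 pre-drug 1 = 3
- First cycle: V4 at about 6 hours 1 + V5, V6, V7 3 + call days 2 and 7 2 = 6
- Second cycle: V8 2 + V9, V10, V11 3 + call days 2 and 7 2 = 7
- V12: 1
- Total: 3 + 6 + 7 + 1 = 17, of which 14 follow the first dose

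**3. Share under the rule.**

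- Per subject: 2/17 = 11.8% of all forms; 2/14 = 14.3% of post-dose forms
- Randomised subjects: full dose 5 × 2 = 10, active placebo 3 × 2 = 6, total 16 of 8 × 17 = 136 (11.8%)
- Lead-in: 2 × 2 = 4. Stage 2: at most 3 × 2 = 6
- Maximum overall: 16 + 4 + 6 = 26

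**4. What reaches the analysis at V6 or V10.**

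| State at the contact | On CRF? | Status under SAP 9.9.4 |
|---|---|---|
| No ideation or behavior | No | Negative |
| Positive, unchanged | No | Positive |
| Positive, lower than before | No | Positive |
| Positive, observed increase | Yes | Positive |

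**5. Conditional size.** Suppose the contact had its own row. Let *q* be the true share positive, *f* the share of positives that are observed increases, and assume every increase is a positive response. Both values are assumptions.

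- Counting CRF forms only, the percentage is 100% whatever *q* is, provided at least one form is entered.
- With all subjects as denominator and absent forms read as negative, it is *q × f*. For *q* = 20%, this gives 2% at *f* = 0.1, 10% at *f* = 0.5 and 20% at *f* = 1.
- On the second convention, one omitted stable positive moves an arm's figure by 1/5 = 20 points (full dose) or 1/3 = 33 points (active placebo).

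These figures show the mechanism only. They do not estimate an error in this trial.

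**6. Cumulative counts.** If an increase is judged against the last entered form and is always noticed, an unentered score cannot exceed one already on the CRF, so a count of subjects positive at any time hardly moves. If the reference is baseline or lifetime, that protection is likely but not assured.

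**7. Nearest entered form.** The first integrative session is 1 day after dosing and sessions are about a week apart, so the second falls near day 8. Under Protocol 5.2.5(a) calls start on day 1, which puts the seventh at about day 7. Protocol 8.2 describes the seven days as following the first integrative session, which gives about day 8. Either way an entered form lies within about a day.

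**The case against.** The best defence is redundancy. The next-day, day-2, day-7 and third-session forms are all entered, and so are observed increases. A stable positive at V6 would very probably appear on the day-7 form. Psychiatric adverse events are collected throughout (Protocol 8.5). The excepted forms stay in source, open to monitoring and inspection (Protocol 11.0). The tables are descriptive for arms of 3 and 5, and SAP 7.0 treats any testing as exploratory. The scoring guide cited in SAP 9.9.4, which is not available here, may settle periods and denominators. All of this stands, and it is why the effect is small. It does not supply a rule that brings the source-only forms into the analysis or excludes the contact from it. Nor do the documents say which rule applies if this session replaces the day-7 call under Protocol 5.2.6(i).

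Three stronger readings are tempting, and the documents do not support them.

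- **That the analysed data are selected on the very outcome tabulated.** The rule selects on an increase and the SAP counts a level. No text shows that this contact has its own row.
- **That entry is skewed between arms.** The therapists record a belief about assignment at the first integrative session (Protocol 5.2.4(d)), but nothing shows that this affects what they record as an increase.
- **That SAP Table 2 removes every integrative-session form.** Footnote J reads "For 7 days post Exp. Session, CSSRS D2 and D7 of calls only" and is attached to the C-SSRS at those visits. It also marks the telephone-contact row, and it reads naturally as limiting which calls carry the scale. SAP 5.0 makes the protocol the definitive reference, so 5.2.4(c) and 5.2.6(c) govern.

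**Conclusion.** The point holds as a modest flaw in safety capture. Protocol 5.1.2 makes database entry at one contact per experimental session depend on an observed increase, and SAP 9.9.4 tabulates levels without allowing for this. It affects 2 of 17 scheduled Stage 1 forms per subject, 16 of 136 in the randomised comparison, and at most 26 in the whole trial. These counts assume the planned enrolment, full attendance and, for the maximum, all three active-placebo subjects entering Stage 2.

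A by-period count or percentage is distorted only if the period includes this contact and a subject's status there is not already represented by another entered form or, for a percentage, the denominator is built from entered forms. No error in percentage points is claimed. Cumulative counts should change little. The matter is worth correcting because the data already exist and the correction is cheap.

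**What to change.** **Preferred.** Delete the exception in Protocol 5.1.2 and enter the second-session forms already held in source. In SAP 9.9.4, state that all administrations are tabulated, list the contacts in each time period, and use all subjects assessed in that period as the denominator. The cost is entry of at most 26 completed forms, a few SAP sentences and a minor protocol amendment. No new assessment is needed.

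**If the protocol is not amended.** Either have SAP 9.9.4 call for the source forms from V6, V10, V16 and V20, which keeps the tables complete at the same data-entry cost; or have it state that second-session records exist only when an increase was observed, and footnote every period that contains them. The second option costs only SAP text but leaves the gap in the data.

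Dropping the contact from the percentages is a poorer choice, because it would remove the observed increases, which are the records of most safety interest.
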